10. STATISTICAL CONSIDERATIONS

10.1 Sample Size

The study is well powered to address all of the specific aims. The primary driver of size is specific aim 1, which involves non-inferiority for death (due to PE or VTE prophylaxis). We plan for a sample size of 12,200.

For specific aim 1, we assume a non-inferiority margin of 0.36%. This margin is derived from a discrete choice experiment in which patients indicated a willingness to accept a 0.08% increased risk of death (due to clots or clot prevention medicine) in exchange for each of a specific set of benefits of taking aspirin over LMWH. These benefits include their preference for (1) oral vs. injectable medicine, (2) decreased risk of bruising, (3) lower out of pockets costs and (4) 1% reduction in complication rates. Given that we expect a 1.5% reduction in the complication rate, we value the fourth benefit as 1.5 times the value of each of the other three benefits. Thus, we set the non-inferiority margin at 0.36% ($0.08\% + 0.08\% + 0.08\% + 1.5 \times 0.08\%$), as the maximum increased risk of death (due to clots or clot prevention medicine) to which the patients would be indifferent given the hypothesized benefits of aspirin over LMHW use.

The PREVENT CLOT study protocol is the confidential intellectual property of the PREVENT CLOT Principal Investigators, Steering Committee, and the University of Maryland Baltimore and METRC and cannot be used in any form without the expressed permission of the Principal Investigators.

We anticipate the rate of clot- and clot prevention medicine-related death to be around 0.25%. However, we also anticipate that a proportion of deaths will be adjudicated as being *potentially* due to clots or clot prevention medicine. If the probability of death (attributable or potentially attributable to either clots or clot prevention) in the LMWH arm is 0.445%, we determined (using simulation) that the proposed sample size will provide (1) an 80% chance of declaring non-inferiority if the probability of death for aspirin is 0.445% (that is, if the probability of death is truly the same in both arms) (2) an 80% chance of declaring harm if the probability of death for aspirin is 1.28%.

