If the probability of death (attributable to either clots or clot prevention) in the LMWH arm is 0.25%, we determined (using simulation) that the proposed sample size will provide (1) greater than a 95% chance of declaring non-inferiority if the probability of death for aspirin is 0.25% (that is, if the probability of death is truly the same in both arms) (2) an 80% chance of declaring harm if the probability of death for aspirin is 1.00%.

For specific aim 2, which involves non-inferiority for PE, we considered power associated with a non-inferiority margin of 0.87%. This non-inferiority margin is highly conservative as patients have expressed a willingness to accept this 0.87% increase in clot complications just for the advantage of oral versus injection medication. Based upon the discrete choice experiment, a non-inferiority of 3.9% ($0.87\% + 0.87\% + 0.87\% + 1.5*0.87\%$) is justifiable. Assuming a probability of PE for LMWH of 1.5% and a loss to follow-up rate of 7.5%, we determined (using simulation) that the proposed sample size will provide (1) greater than a 95% chance of declaring non-inferiority if the probability of PE for aspirin is 1.5% (that is, if the probability of PE is truly the same in both arms) (2) an 80% chance of declaring harm if the probability of PE for aspirin is 3.19%.

With regards to specific aim 3, the planned sample size will provide 80% power to detect risk of infection/bleeding from 10% in the LMWH arm to 8.47% in the aspirin, assuming a 7.5% loss to follow-up rate.

The study is overpowered for all secondary aims.

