8.6 Stopping Rules

The DSMB will review the overall progress of the trial in terms of recruitment, data quality, and event frequency and makes a formal recommendation to PCORI at the end of each scheduled meeting as to whether the trial should continue unmodified, continue with protocol modifications or be stopped.

There are two formal interim analyses and one final analysis planned to assess differences between group with respect to death within 90 days of randomization. The first will occur after one-third of enrolled patients are followed for 3 months. The second will occur after two-thirds of enrolled patients are followed for 3 months. At each interim analysis, the DSMB will evaluate whether there is a difference in mortality rates between groups. Specifically, they will assess whether the absolute difference in the risk of death between aspirin and LMWH is different than zero. At each interim analysis, two-sided confidence intervals for the difference in risk for death will be computed. The overall type I error of the interim monitoring procedure will be controlled by using a 99.6% confidence interval at the first interim analysis, 98.8% confidence interval at the second interim analysis and a 96.2% at the final analysis. If probability of dying is 1% in both arms, the probability of falsely declaring harm using this procedure is less than 5%.

The PREVENT CLOT study protocol is the confidential intellectual property of the PREVENT CLOT Principal Investigators, Steering Committee, and the University of Maryland Baltimore and METRC and cannot be used in any form without the expressed permission of the Principal Investigators.

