10. STATISTICAL CONSIDERATIONS

10.1 Sample Size

The study is well powered to address all of the specific aims. The primary driver of size is specific aim 1, which involves non-inferiority for death. We plan for a sample size of 12,200. Enrollment will continue up to 12,400 to account for the potential removal of post-randomization inappropriate enrollment and late ineligible patients for a total of up to 12,400 to be randomized, but 12,200 included in the final analytic sample.

Our original sample size estimated the baseline rate of PE-related death was 0.25%. A non-inferiority margin of 0.36% was based on the costs and administration benefits of aspirin as calculated from a discrete choice experiment of 232 orthopaedic trauma patients (Haac 2017). Using a noninferiority design, we calculated that a sample size of 12,200 patients would provide more than 95% to show that aspirin was noninferior to LMWH for the prevention of PE-related death. The calculation used an alpha of 2.5% and accounted for two interim analyses and 7.5% attrition.

The PREVENT CLOT study protocol is the confidential intellectual property of the PREVENT CLOT Principal Investigators, Steering Committee, and the University of Maryland Baltimore and METRC and cannot be used in any form without the expressed permission of the Principal Investigators.

After changing the primary outcome from PE-related death to all-cause mortality, the estimated baseline rate increased from 0.25% to 1.0%. A non-inferiority margin of 0.75% was based on the patient-important benefits and a survey of experts and orthopaedic surgeons (Haac 2017). Using a noninferiority design, we calculate that a sample size of 12,200 patients would provide more than 95% to show aspirin was noninferior to LMWH in the preventing death. If the probability of death is 1% in the LMWH arm and 1.75% in the aspirin, the study has less than 2.5% chance of declaring non-inferiority.

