7.4 Analytic Strategy

- We will test Estimand 1 for non-inferiority using the upper bound of a two-sided 96.2% confidence interval compared to the pre-specified non-inferiority margin of 0.75%.
- If non-inferiority is established at our pre-specified non-inferiority margin, we will test for superiority.
- Two-sided 95% confidence intervals will also be presented for Estimands 2-9 but null-hypothesis significance tests will not be performed.

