7.6 Comments

- Due to low event rates, it may be impossible to compute reliable confidence intervals.
- We recognize that precision can be increased by leveraging baseline covariates. To the extent possible, we will leverage age, injury severity, and other key characteristics.

8 Change in Primary Outcome

The primary study outcome was changed from PE-related death to all-cause mortality during the course of the trial.

At the recommendation of an external peer reviewer for the protocol manuscript, the trial's steering committee determined that it was infeasible to adjudicate death due to pulmonary embolism (PE) with reasonable certainty. Misclassification of the primary outcome of PE-related death would bias the results to non-inferiority. As such, the trial's steering committee decided to change the primary outcome from PE-related death to all-cause mortality. All-cause mortality was viewed as more important than PE-related death by our patient stakeholder and protocol committees and had greater scientific reliability. The change in the primary outcome increased the anticipated base rate from 0.25% to 1.00% leading to an increase in the non-inferiority margin from 0.36% to 0.75% to maintain the target sample size of 12,200 and over 90% power. The DSMB was not involved in these decisions due to their masked knowledge of treatment effect from interim analyses. The decision of the trial's steering committee to change the primary outcome and non-inferiority margin was supported by the protocol committee, patient stakeholder committee, and sponsor.

Prepared by:

[name] (ScD), Principal Biostatistician

Approved by:

[name] (MD), Principal Investigator

[name] (PhD), Co-Principal Investigator.

[name] (MD, MPH), Co-Principal Investigator

[name] (MHA), Co-Investigator

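### Is the 0.75% all-cause mortality margin too wide, given the 0.36% excess derived earlier from patient preferences?

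*Combined protocol and SAP*

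**What the plan says.** Protocol version 1.0, section 10.1, had clot- or prophylaxis-related death as the primary outcome, at an expected 0.25%. It built the margin from preference data: 0.08 points of death for each of four benefits of aspirin, the last of them scaled up: "Given that we expect a 1.5% reduction in the complication rate, we value the fourth benefit as 1.5 times the value". The sum, 0.36 points, was described as "the maximum increased risk of death (due to clots or clot prevention medicine) to which the patients would be indifferent".

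Protocol version 11.0, section 10.1, still reports that origin ("A non-inferiority margin of 0.36% was based on the costs and administration benefits of aspirin as calculated from a discrete choice experiment"). It then gives the new basis for all-cause death at an expected 1.0%: "A non-inferiority margin of 0.75% was based on the patient-important benefits and a survey of experts and orthopaedic surgeons". The SAP, section 8, gives a different emphasis: "leading to an increase in the non-inferiority margin from 0.36% to 0.75% to maintain the target sample size of 12,200 and over 90% power". It adds that the protocol committee, the patient stakeholder committee and the sponsor supported the change.

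SAP 7.4 compares the upper limit of a two-sided 96.2% interval with 0.75%, and then: "If non-inferiority is established at our pre-specified non-inferiority margin, we will test for superiority". Separately, protocol 8.6 compares the mortality difference with zero, using "a 99.6% confidence interval at the first interim analysis, 98.8% confidence interval at the second interim analysis and a 96.2% at the final analysis".

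**The concern.** A preference-based margin is an absolute trade: so much extra risk of death for so much convenience and so few complications. Moving to all-cause death adds background deaths to both arms but adds no benefit to aspirin. If the drugs change only clot- or prophylaxis-related deaths, the all-cause difference equals the cause-specific one, and the acceptable excess should have stayed at 0.36 points. Instead it became 0.75, a factor of 0.75/0.36 = 2.08. The current documents give two reasons for this and derive neither.

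At stake is how the headline is read. The protocol ties the margin to patient-important benefits, so a finding of non-inferiority could be taken to mean that patients would accept the excess. No planned step compares the result with 0.36. The tempting remedy is an intermediate step that compares the same upper limit with 0.36% before superiority is tested. Because the hypotheses are nested, it would cost no alpha.

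**Working it through.** **Inputs.** Margin 0.75 points and 96.2% interval, z = 2.0749 (SAP 7.4). LMWH mortality 1.0% and 6,100 per arm (protocol 10.1 and 5.1). Attrition of 7.5% is stated only for the original calculation; applied here it gives 6,100 × 0.925 ≈ 5,642 per arm. Results below are for 6,100 / 5,642 per arm.

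**1. The plan's own figures.** With 1.0% in both arms, SE = √(2 × 0.01 × 0.99 / n) = 0.1802 / 0.1873 points. Power = Φ(0.75/SE − 2.0749) = Φ(2.088) / Φ(1.929) = 98.2% / 97.3%. Counting trials that cross an interim bound as failures gives 97.1% / 96.2% by simulation. At 1.75% against 1.0% the test passes about 2% of the time. The stated power (over 95% in the protocol, over 90% in the SAP) and the stated error (below 2.5%) both hold.

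**2. Does feasibility alone give 0.75?** The margin needed is (2.0749 + z for power) × SE. For 90% power it is 3.3564 × SE = 0.60 / 0.63 points; for 95%, 3.7197 × SE = 0.67 / 0.70. So 0.75 is somewhat wider than the SAP's reason requires.

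**3. What 0.36 contains.** 3 × 0.08 + 1.5 × 0.08 = 0.36. If complications do not fall, the last term drops out and the sum is 0.24. At the same exchange rate, 0.75 would need a fall of (0.75 − 0.24)/0.08 = 6.4 points.

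**4. Pass rate at an excess of 0.36.** For 1.00% against 1.36%, SE = √[(0.01 × 0.99 + 0.0136 × 0.9864)/n] = 0.1955 / 0.2033 points. Φ((0.75 − 0.36)/SE − 2.0749) = 46.8% / 43.8%; exact binomial enumeration gives 47.2% / 44.2%. By formula, an assumed LMWH rate of 0.5% gives 71% / 67% and one of 2% gives 27% / 26%. The limiting case at planned mortality is 82 against 61 deaths of 6,100: difference 0.344, interval −0.060 to 0.749.

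**5. Larger excesses, and the comparison with zero.** LMWH at 1.0%. The last column is simulated, counting a lower limit above zero at either interim or at the final analysis (99.6%, 98.8%, 96.2%).

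| True excess (points) | Passes non-inferiority | Flagged as higher aspirin mortality |
|---|---|---|
| 0.36 | 47% / 44% | 42% / 39% |
| 0.50 | 21% / 19% | 67% / 64% |
| 0.60 | 9% / 9% | 81% / 78% |
| 0.75 | 2% / 2% | 94% / 92% |

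**6. Could 0.36 be tested?** With equal arms at 1.0%, the chance that the upper limit falls below 0.36 is 47% / 44%. For 90% power, n = 3.3564² × 2 × 0.01 × 0.99 / 0.0036² ≈ 17,200 per arm, about 34,400 in all.

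**The case for a change.** The strongest case for a change runs as follows. The protocol and SAP are both current and explain the same number differently. The feasibility reason does not by itself produce 0.75. Under the original rule (0.25% against 0.61%, 98% bound, margin 0.36) the same 0.36-point excess passed only 2.5% of the time. Version 1.0 treated a 0.75-point excess (0.25% rising to 1.00%) as a case that should be detected, with "an 80% chance of declaring harm if the probability of death for aspirin is 1.00" per cent. A noisier outcome is a reason for more patients; it does not alter what patients accept. Committee support without a figure is no derivation.

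The documentation part stands: neither text shows how 0.75 arises. The rest is weaker.

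- Carrying 0.36 over to all-cause death assumes that the drugs affect no other deaths. The protocol's background section itself cites higher all-cause mortality with LMWH than with aspirin after arthroplasty, so the assumption is not neutral.
- At exactly 0.36 points patients are, by definition, indifferent. The 44-47% is therefore a pass rate at the edge of what they accept, and it falls quickly beyond it. A middling pass rate near half the margin is normal in any non-inferiority test.
- The current harm rule flags a 0.75-point excess in 92-94% of trials. It is a different claim from the old one (above zero, where the old rule required above 0.36), but such an excess would not go unnoticed.
- As a ratio the margin became tighter: 1.75/1.00 = 1.75 against 0.61/0.25 = 2.44. This is a minor point, because the test and the preference data are on the absolute scale.

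**Conclusion.** No change to the plan. The margin is a fair trade-off: all-cause death avoids uncertain attribution of cause, and the derived 0.36 would need nearly three times the patients (34,400/12,200 = 2.8). SAP section 8 openly gives sample size and power as the reason. The protocol's benefits and survey are a second ground that can hold alongside it; whether the cited source supports 0.75 cannot be judged from these documents. The choice of rationale alters neither the estimate, the interval nor the decision.

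An added step at 0.36% would bring no gain. It would commit the report to saying that an excess lies within what patients accept, on an outcome they were not asked about. It would rest on a limit that drops to 0.24 if complications do not fall, which the trial itself measures. With truly equal arms at 1.0% mortality it would fail 53-56% of the time. Any reader can compare the upper limit of the primary interval with 0.36 or 0.24, and SAP estimands 2 to 4 report PE and non-PE deaths with intervals, closer to what was elicited.

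What remains is care in wording the report: non-inferiority here means an excess below 0.75 points, and the documents show no patient-derived figure for that value. The rates above assume 1.0% LMWH mortality; the 44-47% would be 26-71% for rates from 2% down to 0.5%.
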